5.3 Criteria for participant early termination

- Pregnancy or breastfeeding (see Section [6.7.1](#))
- Declared intention to become pregnant or begin breastfeeding before confirmation of viral suppression following ART re-initiation
- Request by the participant to withdraw

- Request of the primary HIV care provider
- Participant starts ART switch but is not virally suppressed after approximately 12 weeks (see Section 6.1.3).
- Participant is judged by the investigator to be at significant risk of failing to comply with the provisions of the protocol so as to cause to harm to self or seriously interfere with the validity of the study results.
- Participant relocates and remote follow-up or transfer to another CRS is not possible. (Note: Remote follow-up is allowable only after confirmation of viral suppression after ART re-initiation; see Ab Manual of Operations (MOP) and HVTN 805/HPTN 093 SSP for further detail.)
- CRS determines that the participant is lost to follow-up.
- Investigator decides, in consultation with Protocol Team leadership, to terminate participation (eg, if participant exhibits inappropriate behavior toward clinic staff).
- Any condition where termination from the study is required by applicable regulations

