3.3.2 Transition from Schedule 1, *Monitoring ATI* to Schedule 3, *Follow-up on ART*

For participants on Schedule 1, *Monitoring ATI*, any of the following non-virologic criteria will trigger ART re-initiation and transition to Schedule 3, *Follow-up on ART*:

- Confirmed CD4+ T-cell count < 350 cells/mm³ (ie, on 2 consecutive samples)
- Any HIV-related syndrome (eg, ARS, an opportunistic infection)
- Pregnancy or breastfeeding
- ART re-initiation requested by participant
- ART re-initiation requested by primary HIV care provider or clinical research site (CRS) Investigator of Record (IoR) (eg, if deemed medically necessary)

A confirmatory sample should be drawn at the next visit (within approximately 1-2 weeks) following the first CD4+ T-cell count < 350 cells/mm³ (see HVTN 805/HPTN 093 SSP for details).

3.3.3 Transition from Schedule 2, *ATI monitoring with viremia*, to Schedule 3, *Follow-up on ART*

For participants on Schedule 2, *Monitoring ATI with viremia*, the following virologic criteria will trigger ART re-initiation and transition to Schedule 3, *Follow-up on ART*.

From the Week 0 visit to the Week 24 visit in Schedule 2:

- Viral load remains $\geq 1,000$ copies/mL for ≥ 4 consecutive weeks AND viral load has not dropped 0.5 log from the previous week

This ART re-initiation criterion applies irrespective of missed visits and must take account of VL results $\geq 1,000$ copies/mL experienced by a participant while on Schedule 1. Furthermore, assessing whether participants meet this criterion may require additional visits beyond those scheduled from Week 8 (Visit 48) to Week 24 (Visit 56) in Schedule 2. Ideally, these additional visits will be conducted weekly. These additional visits will be treated as interim visits (for more details, see the HVTN 805/HPTN 093 SSP).

After the Week 24 visit in Schedule 2, the ART re-initiation criterion is:

- Confirmed viral load ≥ 200 copies/mL (ie, on 2 consecutive samples).

A confirmatory sample should be drawn at the next visit (within approximately 1-2 weeks) following the first VL result ≥ 200 copies/mL (see HVTN 805/HPTN 093 SSP for details).

The above virologic ART re-initiation criteria are shown schematically in [Figure 3-1](#).

Figure 3-1 Virologic criteria for transition from Schedule 2 to Schedule 3 (ie, ART re-initiation)

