5.1 Inclusion criteria

1. **Estimated date of HIV-1 acquisition** within 8 weeks of (ie, before or after) having received an HVTN 703/HPTN 081 infusion (see HVTN 805/HPTN 093 SSP)
2. **Initiated ART within 28 weeks** of HVTN 703/HPTN 081 date of HIV-1 diagnosis
3. **Receiving continuous ART for at least 1 year**
 - ART interruptions of up to 7 days in duration and ≥ 90 days prior to enrollment are acceptable.
 - Within- and between-class changes in ART within the previous year are acceptable.
4. If on an NNRTI, **willingness and ability to switch** to a PI- or INSTI-containing regimen for at least 4 weeks prior to ART interruption
5. **Willingness to interrupt ART** for up to 24 weeks or up to the time of meeting ART re-initiation criteria (Section 3.3)
6. **Willingness to re-initiate ART** upon meeting study ART re-initiation criteria
7. **Willingness to use barrier protection** (ie, male or female condoms) for all sexual activity during the ATI and until confirmation of viral suppression following ART re-initiation
8. **Willingness for CRS staff to contact primary HIV care provider** to exchange information regarding HVTN 805/HPTN 093 and participant medical history

9. Site investigator anticipates that a **fully active alternative ART regimen** could be constructed and would be available in the event of virologic failure on the participant's current ART regimen.
10. **Access to a participating CRS** and willingness to adhere to study visit schedule and to be followed for the planned duration of the study
11. Ability and willingness to provide **informed consent**
12. **Assessment of understanding:** volunteer demonstrates understanding of this study; completes a questionnaire prior to enrollment with verbal demonstration of understanding of all questionnaire items answered incorrectly.
13. **Agrees not to enroll in another study** of an investigational research agent for the duration of the participant's trial participation

Laboratory Inclusion Values

Immunology/Virology

14. **HIV-1 infection**, with reactive HIV-1 antibody and any Multispot or Geenius HIV-1/HIV-2 results, documented by the HVTN 703/HPTN 081 HIV diagnostic algorithm
15. **Plasma HIV-1 RNA $\geq 1,000$ copies/mL** by any assay, prior to initiating ART
16. **CD4+ T-cell count ≥ 450 cells/mm³** obtained within 90 days prior to enrollment
17. One **plasma HIV-1 RNA below the lower limit of quantitation (LLOQ)** collected at each of the following:

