 - at screening, within 90 days prior to enrollment; and
 - greater than 9 months prior to the screening HIV-1 RNA

Note: Sites must have results from locally available assays that are approved as standard-of-care by their regional governing bodies.

Hematology

18. **Hemoglobin (Hgb) ≥ 10.0 g/dL**
19. **Absolute neutrophil count (ANC) ≥ 750 cells/mm³**
20. **Platelets $\geq 100,000$ cells/mm³**

Chemistry

21. **Alanine aminotransferase (ALT)** < 2.5 times the institutional upper limit of normal and **direct bilirubin** within the institutional range of normal
22. **eGFR** > 60 mL/min/1.73m²

Reproductive Status

23. **Volunteers capable of becoming pregnant:** negative serum or urine beta human chorionic gonadotropin (β -HCG) pregnancy test performed at the screening visit and prior to enrollment. Persons who are NOT capable of becoming pregnant due to having reached menopause (no menses for 1 year) or having undergone total hysterectomy or bilateral oophorectomy or tubal ligation (verified by medical records) are not required to undergo pregnancy testing.
24. **Reproductive status:** A volunteer who is capable of becoming pregnant must agree to consistently use effective contraception (ie, IUD or hormonal; see [Appendix B](#) and HVTN 805/HPTN 093 SSP) for sexual activity that could lead to pregnancy from at least 21 days prior to enrollment through confirmation of viral suppression following ART re-initiation.
25. **Volunteers capable of becoming pregnant must also agree not to seek pregnancy through alternative methods**, such as artificial insemination or in vitro fertilization, until after confirmation of viral suppression following ART re-initiation.

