6.6 Contraception status

Contraception status is assessed and documented at every scheduled clinic visit from screening through confirmation of viral resuppression following ART re-initiation for a participant who is capable of becoming pregnant and who is sexually active in a way that could cause that participant to become pregnant. Prior to enrollment and until viral resuppression is confirmed following ART re-initiation, staff will ask participants to verbally confirm their use of adequate contraceptive methods (see [Appendix B](#)). A participant who is sexually active in a way that could cause that participant to become pregnant should be reminded at all scheduled clinic visits of the importance of using effective contraception (ie, IUD or hormonal) in addition to barrier protection (ie, condoms) to prevent HIV transmission to sexual partner(s) and should be referred to specific counseling, information, and advice as needed. This reminder should be documented in the participant's study record.

Infertility—including having reached menopause (no menses for 1 year) or having undergone hysterectomy, bilateral oophorectomy, or tubal ligation—must be documented in the participant’s study record.

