6.7 Specific clinical management considerations

6.7.1 Pregnancy or breastfeeding

Volunteers who are pregnant or breastfeeding are not eligible to participate in this study. Participants who become pregnant or are breastfeeding during the ART switch will not be allowed to interrupt ART and will be terminated from the study immediately. Participants who become pregnant or are breastfeeding during the ATI phase will re-initiate ART as soon as possible. Post-ATI follow-up will continue per Schedule 3 for up to 24 weeks after viral re-suppression is confirmed following ART re-initiation.

Participants who become pregnant or begin breastfeeding while on Schedule 3 (ie, after ART re-initiation) will continue per Schedule 3 for up to 24 weeks after viral re-suppression is confirmed.

If a participant completes the study or chooses to discontinue from the study before the pregnancy ends, then CRS staff should request permission to contact the participant regarding pregnancy outcomes at the end of the pregnancy. If obtained, pregnancy outcomes will be recorded on a CRF at the end of the pregnancy. All pregnancies must be reported to the Antiretroviral Pregnancy Registry.

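### Protocol 5.3 lists a declared intention to conceive or breastfeed as a termination criterion in every phase, while 6.7.1 restarts and follows participants who actually do so once ATI has begun

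*Protocol*

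**What the plan says.** Protocol 5.3 has two adjacent bullets on this subject. The first, on actual pregnancy or breastfeeding, refers the reader to 6.7.1. The second stands alone: "Declared intention to become pregnant or begin breastfeeding before confirmation of viral suppression following ART re-initiation". It runs until suppression is confirmed after restart, so it covers all time off ART and the early part of Schedule 3.

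Section 6.7.1 distinguishes three phases for actual pregnancy or breastfeeding:

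- **ART switch.** Someone to whom either happens "during the ART switch will not be allowed to interrupt ART and will be terminated from the study immediately".
- **ATI.** "Participants who become pregnant or are breastfeeding during the ATI phase will re-initiate ART as soon as possible", followed by Schedule 3 for up to 24 weeks after confirmed re-suppression.
- **Schedule 3.** "Participants who become pregnant or begin breastfeeding while on Schedule 3 (ie, after ART re-initiation) will continue per Schedule 3", with the same 24-week limit.

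Sections 3.3.2 and 3.3.3 list pregnancy and breastfeeding as triggers for restart and transition to Schedule 3. They do not list a declared intention. They do list "ART re-initiation requested by participant", and requests by the HIV care provider or the site investigator.

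Under 6.5, someone terminated on Schedule 1 or 2 is urged to restart ART with her own provider.

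**The concern.** Staff are likely to hear of such a plan while the participant is still attending: "Contraception status is assessed and documented at every scheduled clinic visit from screening through confirmation of viral resuppression" (6.6). That is when a supervised restart could be arranged. Section 5.3 instead names termination as the response and does not point to the restart route.

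Three protections are tied to staying in the study.

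- Protocol 2.6 describes accelerated, physician-led access to restart for participants. The reason given is that stock-outs, nurse-led public care and delays of several weeks could cause difficulty.
- The same section describes PrEP for partners for as long as the participant is enrolled.
- Under 11.1.1 the PSRT watches for inadequate virologic response within 12 weeks of restart. A participant who leaves before restart cannot contribute to that check.

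She may also be viremic and planning sex without the barrier protection that inclusion criterion 7 requires "for all sexual activity during the ATI and until confirmation of viral suppression following ART re-initiation". That is a possibility, not something the documents state; inclusion criterion 25 recognises other routes to conception.

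**Working it through.** **The two rules by phase**

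| Phase | Actual pregnancy or breastfeeding (6.7.1) | Declared intention (5.3) |
|---|---|---|
| ART switch, before ATI | Terminated | Termination criterion met |
| ATI, Schedules 1 and 2 | ART restarted, then Schedule 3 | Termination criterion met; requested restart open but not cited |
| Schedule 3, not yet re-suppressed | Schedule 3 continues | Termination criterion met; no offsetting provision |
| Schedule 3, re-suppression confirmed | Schedule 3 continues for up to 24 weeks | Criterion no longer applies |

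The rules agree in the first row. In the second they differ, but a site can close the gap by using 3.3.2 or 3.3.3. In the third a request to restart is no help, because ART has already been restarted.

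A participant who agrees to restart and to wait for confirmed suppression does not meet the bullet. The affected group is those who will not wait.

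**Share of the sample.** The planned size is 16 to 61 (Protocol 1). One exit is 1/16 = 6.3% or 1/61 = 1.6%.

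**Effect on the PSRT check.** Protocol Table 4-2 gives the true event rate with a 90% chance of at least one observed event, which is 1 − 0.1^(1/n). The formula reproduces the table's entries for all enrolled participants: 13.4% at n = 16 and 3.7% at n = 61. The table concerns SAEs; applying it to failure to re-suppress is an assumption made here. With one participant fewer:

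- n = 15: 1 − 0.1^(1/15) = 14.2%, up from 13.4%.
- n = 60: 1 − 0.1^(1/60) = 3.8%, up from 3.7%.

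**What is lost for the individual.** Appendix G totals 78 mL for viral load at 6 mL each, so 78/6 = 13 samples, at Visits 80 to 92. Visit 80 is drawn before restart (footnote 7). The samples within 12 weeks after restart are at Weeks 2, 4, 6, 8, 10 and 12, which are Visits 81 to 86: six in all. Someone who leaves before restart has none of the six observed in the study. Someone who leaves during early Schedule 3 loses only those still to come; an exit just after Week 4, for example, loses four of six.

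**The case against.** The strongest reply is that the safeguard already exists. Sections 3.3.2 and 3.3.3 make a request from the participant, her provider or the investigator sufficient for restart and transfer to Schedule 3. A site can use that route without any amendment. Section 5.3 is a list of criteria, and it does not say that termination is automatic or must come before restart. Where the protocol means immediate termination, as for the ART switch in 6.7.1, it says so. **This part stands.** A reader might infer that a participant who declares the intention during ATI must be discharged while off ART. The documents do not support that: they allow it but do not require it.

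A second reply is that the difference is deliberate. Actual pregnancy brings exposure of a fetus and a need for outcome follow-up. Someone who will not wait is departing from her entry commitments on contraception (inclusion criterion 24) and on seeking pregnancy: "Volunteers capable of becoming pregnant must also agree not to seek pregnancy through alternative methods". **This partly stands.** It is a reason to end the interruption. It does not explain ending observation before re-suppression, particularly when 3.3.4 urges even a participant who refuses restart to keep attending.

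A third reply is that the Study Specific Procedures may settle the handling. Section 6.5 refers to them for further detail on these exits. Neither they nor the consent pages are available here, so the point is limited to the protocol's own wording.

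Finally, termination does not mean that care stops. Section 6.5 provides for a termination visit and for urging restart, and inclusion criterion 8 lets the site contact the HIV care provider. What is lost is observation and support within the study; the documents do not show that treatment would be absent.

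**Conclusion.** The inconsistency holds, and it is minor. Once ATI has begun, the protocol's listed response to a declared intention is less protective than its response to the event itself. During Schedules 1 and 2 the gap is one that sites can bridge but are not told to. On Schedule 3 before confirmed re-suppression, the protocol offers no offset.

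The documents give no frequency. The contraception and pregnancy-seeking commitments in inclusion criteria 24 and 25 make the situation probably rare.

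It would be tempting to read this as a threat to the trial's safety conclusions. The figures do not support that: the detectable rate moves by 0.8 percentage points at the smallest planned size and by 0.1 at the largest. The 12-week check is a PSRT monitoring item and is not named in primary endpoint 2 (3.2.1). The consequence is for the individual participant.

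This conclusion assumes that the bullet refers to an intention to conceive or breastfeed before re-suppression is confirmed, and that the unseen study procedures do not already direct sites to restart and follow-up.

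**What to change.** Amend the 5.3 bullet and cross-refer it to 3.3.2, 3.3.3, 3.3.4 and 6.7.1, so that:

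- Termination for declared intention applies only before ATI starts. By the enrollment definition in 6.1.2, that is the ART-switch period.
- Once ATI has started, a declared intention leads to prompt restart through the existing participant- or investigator-request trigger, then to Schedule 3 follow-up, with consent, at least until re-suppression is confirmed.
- If she declines to restart, 3.3.4 applies.
- A participant already on Schedule 3 continues on it.

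The cost is a change to one bullet and its cross-references, with no new procedures. The burden is up to 7 already scheduled visits (80 to 86) for a participant who is re-suppressed by Week 12.

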5.4 Study termination

This study may be terminated early by the determination of the HVTN 805/HPTN 093 PSRT, a pertinent national regulatory authority, NIH, or the Office for Human Research Protections (OHRP). In addition, the conduct of this study at an individual Network CRS may be terminated by the determination of the IRB/EC and any applicable RE.

6 Study procedures

For all study visits, unless otherwise specified, participants will come to their assigned CRS.

6.1 Schedule 1: Monitoring ATI

6.1.1 Screening

Screening may occur over the course of several contacts/visits. All inclusion and exclusion criteria must be assessed within 8 weeks (56 days) prior to enrollment, unless otherwise specified in the eligibility criteria (Section 5).

After signing informed consent, volunteers will undergo the following procedures, as shown in [Appendix E](#) and [Appendix H](#):

- Assessment of Understanding
- Medical history, including:
 - current psychiatric status and history
 - assessment of routine clinically-indicated vaccinations (note: must be completed prior to ATI initiation (see Section 5.2))
- Complete physical examination
- Assessment of concomitant medications
- HIV transmission risk behavior assessment and counseling
- Contraception status assessment (for participants who are capable of becoming pregnant and who are sexually active in a way that could lead to pregnancy; see 6.6 and [Appendix B](#))
- Decision aid
- Blood collection for:
 - HIV PCR viral load
 - CD4+ and CD8+ T-cell counts
 - HBsAg and hepatitis C serology
 - QuantiFERON TB test

- Hgb, ANC, platelets
- ALT, direct bilirubin, eGFR
- Syphilis testing
- Urine pregnancy test (persons not of reproductive potential due to having reached menopause (no menses for 1 year), or having undergone hysterectomy or bilateral oophorectomy or tubal ligation [verified by medical records], are not required to undergo pregnancy testing)
- Gonorrhea/chlamydia testing by urine or cervical/vaginal swab
- Trichomonas testing by cervical/vaginal swab
- Tuberculin skin test (TST; only if QuantiFERON TB test not available)

6.1.2 Enrollment

- Participants undergoing an “ART switch” will be considered enrolled on the first day of the new ART medication.
- Participants who do not undergo an “ART switch” will be considered enrolled at the initiation of ATI (Day 0).

6.1.3 ART Switch

ART switch

Participants taking NNRTI-based ART regimens are required to switch to a PI- or INSTI-based regimen at least 4 weeks before beginning ATI and must demonstrate viral suppression (ie, < LLOQ) on the new regimen before beginning ATI.

At the clinic visit initiating the ART switch, the participant will undergo the following procedures (see [Appendix E](#) and [Appendix H](#)):

- Targeted (ie, symptom directed) physical examination, including weight and vital signs
- Assessment of concomitant medications
- Intercurrent illness/adverse experiences (AEs)
- HIV transmission risk behavior assessment and counseling

- Contraception status assessment (for participants who are capable of becoming pregnant and who are sexually active in a way that could lead to pregnancy; see Section 6.6 and [Appendix B](#))
- Decision-making assessment
- Psychosocial assessment
- Blood collection for:
 - HIV PCR viral load
 - CD4+ and CD8+ T-cell counts
 - Hgb, ANC, platelets
 - ALT, direct bilirubin, eGFR
- Urine pregnancy test (persons not of reproductive potential due to having reached menopause (no menses for 1 year), or having undergone hysterectomy or bilateral oophorectomy or tubal ligation [verified by medical records], are not required to undergo pregnancy testing)

Post-ART switch contact

The site will make arrangements to contact the participant approximately 2 weeks after initiation of the new ART regimen to assess tolerability of the ART switch and willingness to continue. This contact may be conducted over the phone or in person; see HVTN 805/HPTN 093 SSP for details.

ATI qualification visit

Four weeks or more after initiation of the new ART regimen, participants undergoing an ART switch will return for a clinic visit during which they will undergo the following procedures (see [Appendix E](#) and [Appendix H](#)):

- Targeted (ie, symptom directed) physical examination, including weight and vital signs
- Assessment of concomitant medications
- Intercurrent illness/adverse experiences (AEs)
- HIV transmission risk behavior assessment and counseling
- Contraception status assessment (for participants who are sexually active in a way that could lead to pregnancy; see [Appendix B](#))

- Blood collection for:
 - HIV PCR viral load
 - CD4+ and CD8+ T-cell counts
 - Hgb, ANC, platelets
 - ALT, direct bilirubin, eGFR
- Urine pregnancy test (persons not of reproductive potential due to having reached menopause (no menses for 1 year), or having undergone hysterectomy or bilateral oophorectomy or tubal ligation [verified by medical records], are not required to undergo pregnancy testing)

The procedures for the ATI qualification visit should be repeated as appropriate until viral suppression (ie, < LLOQ) is demonstrated. In general, ATI should be initiated approximately 2 weeks after the ATI qualification visit at which samples are collected that demonstrate viral suppression on the new ART regimen.

Any participant who is not virally suppressed at the ATI qualification visit will be retested on a weekly basis until virally suppressed. If not virally suppressed by approximately 12 weeks from the start of the ART switch, the participant should be referred to re-initiate their previous NNRTI-containing regimen, will not proceed to the ATI, and will be terminated from the study.

